#### 4.4.1 Subject Withdrawal Criteria

All subjects reserve the right to withdraw from the clinical study at any time, as stated in the informed consent form (ICF). The Investigator may discontinue subjects from the clinical study for any of the following reasons:

- ECG evidence of QT prolongation (QTcF > 530 msec, or an increase of QTcF > 60 msec above baseline to a value > 480 msec on the 12-lead ECG, confirmed on a repeat 12-lead ECG taken after resting at least 5 minutes in a supine or semi-recumbent position after the original finding of prolonged QTcF).
- 2. It is the Investigator's opinion that it is not in the subject's best interest to continue in the study.
- 3. Any subject who exhibits any Suicidal Behavior or Suicidal Ideation (e.g. subject answers "yes" to question 4 or 5 in the Suicidal Ideation section of the CSSRS). These subjects should be evaluated by a psychiatrist immediately.

- 4. Rash that is clinically significant and considered to be related to the study drug (e.g. morbiliform, urticarial, papular).
- 5. Subject experiences an SAE considered to be related to the study drug

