7.8.5.2 Clinical Safety Laboratory Evaluations

The name and address of the central clinical laboratory for this study will be maintained in the Investigator's files at each study site.

All clinical laboratory assays will be performed according to the laboratory's normal procedures as described in Table 1 or 2.

Reference ranges are to be supplied by the laboratory and will be used to assess the clinical laboratory data for clinical significance and out-of-range pathological changes. The investigator should assess out-of-range clinical laboratory values for clinical significance, indicating if the values are clinically significant or not. Abnormal clinical laboratory values, which are unexpected or not explained by the subject's clinical condition, may, at the discretion of the investigator or sponsor, be repeated as soon as possible until confirmed, explained, or resolved.

The following clinical laboratory assessments will be performed:

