### 8.4 Analysis Time Point/Visit Windows

For data summarized on a per time point or per visit basis, the windows used for analyses are defined below unless stated otherwise.

Protocol Visit	Window Description (Target Day/Time Point)	Protocol Window (with respect to Visit Day as defined in the protocol)	Analysis Window (with respect to Study Day and Study Time in minutes as defined in this SAP)
Screening	Screening	Day -14 to -1	Study Day < -1
Day 0	Day 0 (Admission)	Day 0	Study Day = -1
Day +1	Day 1 (Pre-Infusion)	N/A	Study Day = 1 and Study Time < 0
Day +1	Day 1 (+4h)	N/A	0 <= Study Time < 360
Day +1	Day 1 (+8h)	N/A	360 <= Study Time < 600
Day +1	Day 1 (+12h)	N/A	600 <= Study Time < 900
Day +1	Day 1 (+18h)	N/A	900 <= Study Time < 1260
Day +2	Day 2 (+24h)	N/A	1260 <= Study Time < 1680
Day +2	Day 2 (+32h)	N/A	1680 <= Study Time < 2160
Day +2	Day 2 (+40h)	N/A	2160 min <= Study Time < 2640 min
Day +3	Day 3 (+48h)	N/A	2640 min <= Study Time < 3120 min
Day +3	Day 3 (+56h)	N/A	3120 min <= Study Time < 3480 min
Day +3	Day 3 (+60h)	N/A	3480 min <= Study Time < 3960 min
Day +4	Day 4 (+72h)	N/A	3960 min <= Study Time < 2 days after 72 hr timepoint

For the IV only cohorts (cohorts 1-5), the following analysis time points and visit windows will be used.

PRS 005 T 17 F

Strictly Confidential. © 2004-2015, PRA Health Sciences. All rights reserved.

Page 16 of 35

Protocol Visit	Window Description (Target Day/Time Point)	Protocol Window (with respect to Visit Day as defined in the protocol)	Analysis Window (with respect to Study Day and Study Time in minutes as defined in this SAP)
Day 11	Day 11	Day 8 to 14	5 <= Study Day < 23
Day 34	Day 34	Day 29 to Day 39	23 < Study Day < 45

For the IV to oral cohort (cohort 6), the following analysis time points and visit windows will be used.

Protocol Visit	Window Description (Target Day/Time Point)	Protocol Window (with respect to Visit Day as defined in the protocol)	Analysis Window (with respect to Study Day and Study Time in minutes as defined in this SAP)
Screening	Screening	Day -14 to -1	Study Day < -1
Day 0	Day 0 (Admission)	Day 0	Study Day = -1
Day +1	Day 1 (Pre- Infusion)	N/A	Study Day = 1 and Study Time < 0
Day +1	Day 1 (Post- Infusion)	N/A	Study Day = 1 and Study Time >= 0
Day 2	Day 2 (Discharge)	N/A	Study Day = 2
Day 4	Day 4 (HAMD Call)	Day 3 to 5	3 <= Study Day <= 5 for HAMD only
Day 8	Day 8	Day 6 to 10	6 <= Study Day <= 9 for HAMD, 3 <= Study Day <= 11 otherwise

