Day 11	Day 11 (HAMD Call)	Day 10 to 12	10 <= Study Day <= 12 for HAMD only
Day 15	Day 15	Day 12 to 18	13 <= Study Day <=18 for HAMD, 12 <= Study Day <= 18 otherwise
Day 22	Day 22	Day 19 to 25	19 <= Study Day <= 25
Day 29	Day 29	Day 26 to 32	26 <= Study Day <= 32
Day 36	Day 36	Day 33 to 39	33 <= Study Day <= 46
Day 57	Day 57	Day 54 to 60	47 <= Study Day <= 64
Day 71	Day 71	Day 68 to 74	65 <= Study Day <= 77

The analysis windows are aligned with, but wider than, those specified by the schedule of visits and procedures in the protocol in order to include in analyses of all study data (including unscheduled visit data) that fall outside of protocol visit windows. If multiple data points are observed within a single analysis window, the latest observation will be used for analysis.

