#### 12.5.3 Exploratory Efficacy Endpoints and Analyses

#### PRS 005 T 17 F

# 12.6 Safety Analyses

Unless otherwise stated in the subsections below, the following safety variables will presented in listings and analyzed in summary tables containing summary statistics and change from baseline by treatment arms for each study time point. All safety analyses will be based on the Safety Set.

- 1) Laboratory measures, including urine drug screen
- 2) Vital signs
- 3) Electrocardiogram (ECG)
- 4) Stanford Sleepiness Scale (SSS).

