### 12.6.4.2 12-Lead ECG

12-lead ECG parameters will be analyzed and transferred externally to PRA. These parameters will be summarized as continuous variables. In addition to summary tables PCS ECG observations will be flagged in data listings based on the criteria given in Table 4.

ECG Parameter	Unit	Low PCS Criteria	High PCS Criteria
Heart rate	bpm	≤50 and decrease of ≥15 from baseline	≥120 and increase of ≥15 from baseline
PR Interval	ms	<120 and baseline value ≥120	>210 and baseline value ≤200
QRS Complex	ms	None	>110 and baseline value ≤110
QTcF	ms	None	Prolongation >30 from baseline

TABLE 4. ECG PCS CRITERIA

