### 12.6.4.5 Columbia-Suicide Severity Rating Scale (C-SSRS)

For the 5 suicidal ideation questions ("Wish to be dead," "Non-specific active suicidal thoughts," "Active suicidal ideation with any methods (not plan) without intent to act," "Active suicidal ideation with some intent to act, without specific plan," "Active suicidal ideation with specific plan and intent") and the 5 suicidal behavior questions ("Preparatory acts or behavior," "Aborted attempt," "Interrupted attempt," "Suicide attempt," "Suicide behavior") of the C-SSRS, the number of subjects who answered "yes" will be tabulated for each applicable study time point. Other data collected on the C-SSRS (e.g., ideation intensity measures) will be provided in data listings only.

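### SAP 8.4's latest-value rule also governs safety data, so a normalised repeat or a later C-SSRS 'no' can displace an abnormal finding from the by-arm tables

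*SAP*

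**What the plan says.** SAP 8.4 sets a general scope: "For data summarized on a per time point or per visit basis, the windows used for analyses are defined below unless stated otherwise". The windows are wider than the protocol's "in order to include in analyses of all study data (including unscheduled visit data) that fall outside of protocol visit windows". Where several values share a window, one rule decides: "If multiple data points are observed within a single analysis window, the latest observation will be used for analysis".

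For labs, vital signs, ECG and the sleepiness scale, SAP 12.6 plans "summary tables containing summary statistics and change from baseline by treatment arms for each study time point". For the ten C-SSRS ideation and behaviour questions, SAP 12.6.4.5 says "the number of subjects who answered 'yes' will be tabulated for each applicable study time point". No safety section gives a different rule for choosing among values.

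SAP 12.6.2 and 12.6.3 flag out-of-range labs and potentially clinically significant (PCS) vital signs in listings. SAP 12.6.4.2 does the same for ECG: "In addition to summary tables PCS ECG observations will be flagged in data listings". Appendix 3 lists no worst-value, shift, PCS-incidence or any-time C-SSRS table.

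Four provisions can create a second value:
- Protocol 7.8.5.2: unexpected or unexplained abnormal labs may, at the investigator's or sponsor's discretion, "be repeated as soon as possible until confirmed, explained, or resolved".
- Protocol 4.4.1: the QTcF withdrawal criterion must be "confirmed on a repeat 12-lead ECG taken after resting at least 5 minutes".
- Protocol 8.1.5: lab, vital-sign or ECG abnormalities new at the end of treatment should be investigated until they are back in range or explained.
- SAP 8.2: women who leave the study during the inpatient phase have the +72h assessments at exit, and these are allocated by window.

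**The concern.** For efficacy, two values in one window are mostly an accident of scheduling. For safety they often are not, because the second value may exist only because the first was abnormal. Keeping the last value then selects in one direction: a normal first value is seldom repeated, while an abnormal one may be replaced by a normal one.

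C-SSRS has a further problem. Protocol Appendix 2 names the baseline and since-last-visit forms. A later 'no' therefore reports a later interval and does not withdraw an earlier 'yes'. Replacing the 'yes' removes a reported event from the table.

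SAP 12.0 gives the study's purpose as finding a dose and exposure that are safe and well tolerated. The by-arm safety tables are therefore a main product of the trial.

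**Working it through.** The plan gives no figure to reproduce on this point. The check reads the sections against each other and then does some window arithmetic.

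**1. Does the rule reach safety data?** SAP 8.4 covers everything summarised by time point unless stated otherwise, and SAP 12.6 summarises safety by time point and states nothing otherwise. It does.

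**2. Would a repeat fall in the same window?** Time left = upper window limit − target, from the SAP 8.4 tables.

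| Time point | Calculation | Left after target |
|---|---|---|
| +12h | 900 − 720 = 180 min | 3 h |
| +24h | 1680 − 1440 = 240 min | 4 h |
| +48h | 3120 − 2880 = 240 min | 4 h |
| +72h | ends 2 days after target | 48 h |
| Day 11, Cohorts 1-5 | 22 − 11 | 11 days |
| Days 8, 15, 29, Cohort 6 (non-HAMD) | 11 − 8; 18 − 15; 32 − 29 | 3 days each |
| Day 57, Cohort 6 | 64 − 57 | 7 days |

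A confirmatory ECG taken after a short rest normally falls in the same window. Lab repeats can do so at the day-based visits. The +48h lab in Cohorts 1-5 is largely protected: a repeat more than 4 h after target falls in a later window and leaves the first value in place.

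**3. Early exit.** A woman who leaves the study at 14 h has exit assessments at 14 × 60 = 840 min. That lies in the +12h window (600 to under 900), so her exit ECG and C-SSRS replace the values taken at +12h. No discretionary repeat is needed.

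**4. C-SSRS.** The Day 11 window in Cohorts 1-5 holds Study Days 5 to 22, which is 22 − 5 + 1 = 18 days. If a woman answered 'yes' on Day 11 and 'no' at an unscheduled interview on Day 14, the table would count 'no'.

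**5. Effect of one replacement on an arm mean.** Shift = (first − repeat) / n. Cohorts of 10 to 30 randomised 1:1 give n of about 5 to 15. Assume a first QTcF change of +60 ms (a reading must exceed this to meet the criterion), a repeat of +5 ms, and zero change in everyone else.
- n = 5: 60/5 = 12.0 becomes 5/5 = 1.0; shift 11.0 ms
- n = 10: 6.0 becomes 0.5; shift 5.5 ms
- n = 15: 4.0 becomes 0.3; shift 3.7 ms

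**6. Average effect on QTcF under the protocol's trigger.** Protocol 4.4.1 asks for a repeat when QTcF exceeds 530 ms, or rises more than 60 ms to above 480 ms. Assume normal readings with per-reading SD s, true mean rise r and one repeat for every rise above 60 ms. Ignore the 480 ms condition, which makes repeats rarer, and the 530 ms alternative. The change from baseline has SD σ = s√2. With z = (60 − r)/σ, the share repeated is P(Z > z). Both readings use the same baseline, so the repeat regresses halfway to r and the mean falls by 0.5·σ·φ(z).
- s = 10, r = 15: σ = 14.1, z = 3.18; share about 0.07%, mean shift about 0.02 ms
- s = 14, r = 20: σ = 19.8, z = 2.02; share about 2.2%, mean shift about 0.5 ms
- s = 6, r = 10: z = 5.9; practically none

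On average the QTcF effect is small. It matters when an event occurs in a small arm.

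**The case against.** Much of the opposing case stands.

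- **Repeats need not normalise.** Lab repeats are optional and may end as confirmed or explained. A confirmed abnormality, including a confirmed QTcF prolongation, stays in the table. A reader might infer that the tables systematically show recovered values; the documents support only that they can.
- **QTcF.** A reader might take the SAP's 30 ms PCS limit as the repeat trigger. In the setting s = 10, r = 15, that would have about 14.5% of women repeated. The 30 ms limit is only a listing flag, and no section ties a repeat to it.
- **C-SSRS.** Protocol 4.4.1 asks for immediate psychiatric evaluation after such answers but orders no repeat interview. A second interview in the window would come from an unscheduled contact or an early exit, and its frequency is unknown.
- **Wide windows come after treatment.** Infusion ends at 60 h in Cohorts 1-5, and the Cohort 6 taper ends on Day 31. No ECG is scheduled in the widest windows, Day 11 and Day 34 in Cohorts 1-5 and Day 57 in Cohort 6. C-SSRS is scheduled in all of them, and labs at Day 11 and Day 57.
- **Adverse events.** Protocol 7.8.5.1 and 7.8.5.4 require clinically significant ECG and vital-sign findings to be recorded as AEs, and Protocol 9.5.7 sends potentially clinically important findings to the AE summaries. The TEAE tables are by arm and use no windows. This limits the loss but does not close it. Protocol 8.1.5 leaves it to the investigator whether a changed value is an AE, and SAP 12.6.1 contains no step that turns a PCS value or a C-SSRS 'yes' into one.
- **Listings.** With so few women per arm, flagged listings can be read subject by subject. The data are kept; what is missing is a by-arm count.

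**Conclusion.** The point holds as a possibility built into the plan. Followed as written, SAP 8.4 can replace an abnormal lab, vital-sign or ECG value with a normalised repeat in the same window, and can replace a C-SSRS 'yes' with a later 'no'. No planned by-arm table other than the TEAE tables would show the displaced finding, and those show it only if it was recorded as an AE. C-SSRS is the strongest case, because the later answer covers a different interval.

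The documents do not allow a rate to be stated. One replaced reading can move a small arm's mean by several milliseconds under the assumed values. The average QTcF effect under the protocol's own trigger is 0.5 ms or less across the assumed settings.

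A reader might also infer that dose escalation was misled. The documents do not support that: SAP 4.0 and 10.1 place the Data Review Committee's analyses in a separate document.

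The change should be made, because the rule leans one way on the trial's main question and the remedy is cheap.

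**What to change.** Amend SAP 8.4, 12.6 and Appendix 3 as follows.

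1. **C-SSRS:** count a question as 'yes' for a window if any interview in that window is 'yes', and add a by-arm row for 'yes' at any time post-baseline.
2. **Worst post-baseline:** add by-arm rows, at any time and including unscheduled values, for out-of-range labs and for the vital-sign and ECG PCS criteria.
3. **By-visit safety means:** use the valid scheduled assessment where there is one, and exclude invalid samples such as hemolysed ones. Simply taking the first value in the window would be weaker. It could keep a bad sample, and SAP 8.2 already lets baseline be the last pre-dose value, repeats included.
4. **Efficacy:** keep the latest-value rule.

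The cost is SAP wording and a few table rows from data already collected. Abnormality rates will look slightly less favourable and will include some unconfirmed readings, which a footnote can mark.

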# 9.0 Analysis Sets

The **Screened Set** will consist of all subjects who have signed an informed consent.

The Randomized Set will consist of all subjects who were randomized.

The **Safety Set** will consist of all subjects who received IP.

The **modified Intent to Treat Set** (mITT) will consist of all subjects in the Safety Set who have at least 1 post-randomization efficacy assessment.

The **Per Protocol (PP) Set** will consist of all subjects in the mITT set who do not have protocol deviations that may affect key efficacy endpoints.

The **Infusion Completer Set** will consist of all subjects in the IV only cohorts (cohorts 1-5) who completed the 60-hour infusion and all subjects in the IV to oral cohort (cohort 6) who completed the initial infusion.

The **Completer Set** will consist of all subjects in the IV only cohorts who completed the 60-hour infusion and attended all outpatient visits, and all subjects in the IV to oral cohort who completed the initial infusion and oral IP dosing period with at least 80% oral dosing compliance and attended all outpatient visits.

Subjects in the Safety Set will be analyzed according to the actual treatment received. Subjects in the Randomized, mITT, and both completer sets will be analyzed according to assigned treatment regardless of actual treatment received.

# 10.0 Analyses

# 10.1 Data Review Committee (DRC)

Interim unblinded analyses of safety and efficacy data will be conducted by a Data Review Committee (DRC) during the study, separate from the blinded study team. The DRC is composed of the Marinus Chief Medical Officer and at least two other external physicians. At least one of the members will have special expertise in the clinical care of women with depression or postpartum depression. One of the members will have expertise in the conduct of clinical trials and analysis of clinical trial data. Additional expert members will include an independent contractor statistician (DRC statistician) and a pharmacokineticist).

It is the DRC's responsibility to weigh the risks and benefits of ganaxolone after each interim analysis and make a recommendation on whether the study or cohort should be continued or stopped. The DRC will also provide a recommendation for the next dosing regimen with the goal of gaining additional information on ganaxolone's tolerability and dose-response profile. A separate DRC guidance document outlines the principles for dose selection. Marinus may decide to stop the study, or make the data public, after completion of any cohort.

For the purpose of the DRC meetings, a snapshot of the clinical trial database will be delivered to the DRC statistician who will generate necessary tables, figures and listings (TFLs) needed for the DRC data review. These analyses will be specified in a separate document agreed upon between the DRC and Marinus. The randomization list will be delivered directly to the DRC statistician, who will perform unblinding. The Marinus and PRA study teams will remain blinded until after each cohort database lock.

Pharmacokinetic data will be transferred to the DRC pharmacokineticist directly from the pharmacokinetic analysis vendor (QPS Inc) using a password protected file.

The TFLs generated for the DRC meetings are separate from the TFLs prepared following each database lock, as described below.

PRS 005 T 17 F

# 10.2 Analyses After Cohorts 1-3

An unblinded analysis of efficacy and safety data for Cohorts 1-3 will be conducted after the last patient in Cohort 3 has completed her final visit (or withdrawn from the study), all clinical data have been entered into the data capture system, AE and concomitant medication data have been coded, quality control checks have been completed, all data queries have been resolved, protocol deviations and the per protocol analysis set have been identified, and the database has been locked. TFLs for subject disposition, demographics and baseline characteristics, efficacy, and AEs will be produced external to PRA.

The continuing trial subsequent to Cohort 3 will again be conducted in a double-blind fashion.

# 10.3 Final Analysis

The unblinded final analysis will occur when all subjects in the final cohort have completed their final visit (or withdrawn from the study), all clinical data have been entered into the data capture system, AE and concomitant medication data have been coded, quality control checks have been completed, all data queries have been resolved, protocol deviations and the per protocol analysis set have been identified, and the database has been locked. However, Sponsor may decide to stop the study, or make all or a portion of the data public, at any time during any cohort.

If Sponsor chooses to unblind and/or make public all or any portion of the data before database lock, the following processes will be in place:

- A cutoff date or study visit will be established, referred to as the "cutoff time point."
- A database freeze procedure will be performed in a blinded manner for data collected up to and including the cutoff time point. Documentation of the database freeze procedure will include a detailed description of the specific data that were cleaned prior to the freeze, the timing of temporarily eliminating site access to the database for additional data entry during the freeze, the duration of the freeze, the specific portions of the database that will be unfrozen so that data entry can continue, and procedures for validating that the data up to and including the cutoff time point were not changed post freeze.
- Key personnel required to produce SDTMs, ADaMs, and TFLs will be unblinded at the subject level after database freeze. This will include programmers and statisticians but not other members of the data management team, nor any other members of the clinical team, nor any other representatives of Sponsor. Specific personnel who are unblinded at this stage will be documented. Data listings produced for quality control purposes will not display unblinded treatment assignments from cohorts for which hard lock has not yet occurred.
- Any data summaries or other trial-level data presentations containing unblinded data will consist only of data from the frozen portion of the database until the complete database has been locked.
- Any study personnel with exposure to unfrozen, unblinded data prior to database lock will not be involved in decisions that result in changes to the data or the analysis plan until the complete database has been locked and the study has been formally unblinded.
- Three sets of summaries and analyses will be produced: (1) a topline set that includes data only up to and including the cutoff time point to be delivered before database lock and formal unblinding, (2) the same topline set rerun and revalidated after database lock and formal

unblinding, and (3) a complete set that includes all data, to be delivered after database lock and formal unblinding.

 Analyses of primary and secondary endpoints will consist only of data up to and including the cutoff time point. Any analysis that includes data that were not part of the frozen portion of the database will be exploratory.

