# 4.0 Introduction

This SAP should be read in conjunction with the study protocol and case report form (CRF). This SAP amendment is based on Protocol Version 8.0, Amendment 7 dated 08Oct2018 and CRF dated 09Aug2018. Any further changes to the protocol or CRF may necessitate updates to the SAP.

Analyses presented to the Data Review Committee (DRC), as well as the pharmacokinetic (PK) and neurosteroid analyses, will not be detailed in this SAP.

This SAP supersedes the statistical considerations identified in the protocol; where considerations are substantially different, they will be so identified in Section 4.1. Any post-hoc or unplanned analyses not included in this SAP, or significant changes from the planned analysis in this SAP, will be clearly identified in Section 9.8.2 of the clinical study report (CSR). Changes to planned analyses after database lock do not require an updated SAP but should be included in the CSR.

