#### 12.5.2 Secondary Efficacy Endpoints

The trial will also evaluate the following secondary endpoints at each post-baseline data collection time point to provide additional evidence of the efficacy of ganaxalone in treating PPD:

- Change from baseline in HAMD17 total score other than at 60 hours post-infusion (on Day 3) for Cohorts 1-3 and to Day 29 for Cohort 6
- HAMD17 response defined as at least a 50% reduction from baseline in total score
- HAMD17 remission defined as total score <= 7
- Change from baseline in EPDS total score
- Change from baseline in STAI6
- CGI-I rating

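### SAP 10.3 permits publication and unblinding during a running cohort with no earliest cutoff, in undeclared conflict with the protocol and SAP 10.1

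*SAP*

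**What the plan says.** SAP 10.3 first places the final analysis after database lock, then adds an exception: "Sponsor may decide to stop the study, or make all or a portion of the data public, at any time during any cohort". If the sponsor unblinds or publishes before lock, a set of steps applies. The first is "A cutoff date or study visit will be established"; no earliest date, visit or number of subjects is given. A blinded database freeze follows. Documented programmers and statisticians are then unblinded at subject level, to the exclusion of other clinical-team members and sponsor representatives. Personnel exposed to unfrozen, unblinded data "will not be involved in decisions that result in changes to the data or the analysis plan" until lock and formal unblinding. A topline set is produced, rerun after lock, and followed by a complete set.

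The section closes with two rules on status: "Analyses of primary and secondary endpoints will consist only of data up to and including the cutoff time point" and "Any analysis that includes data that were not part of the frozen portion of the database will be exploratory".

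SAP 10.1 allows publication after completion of a cohort and states: "The Marinus and PRA study teams will remain blinded until after each cohort database lock". SAP 4.0 says that it supersedes the protocol's statistical considerations and that "where considerations are substantially different, they will be so identified in Section 4.1".

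**The concern.** The SAP gives two answers on when data may be released, and the more permissive one contradicts the protocol. Because the SAP overrides the protocol on statistical matters, a reader could take the permissive rule as the operative one, although it is not among the declared changes.

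The two status rules make this more than a publication-policy question. Together with an unrestricted cutoff, they determine which subjects form the primary comparison. SAP 12.5.1 gives a 3-4 point difference in mean HAMD17 change the greatest weight in judging efficacy, and protocol 2.1 uses the study to choose a dose and regimen for further development. An estimate from part of a cohort could be published as the primary result, with the full-cohort estimate relegated to exploratory status.

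**Working it through.** **Passages side by side**

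| Question | SAP 10.3 | Elsewhere |
|---|---|---|
| When may data be made public? | During any cohort | After completion of a cohort: protocol 3.7, 9.5.1, 10.5; SAP 10.1. Protocol 3.8: completion is the final subject's final assessment, follow-up included |
| Who is unblinded, and when? | Named programmers and statisticians, before lock | SAP 10.1: sponsor and CRO study teams blinded to each cohort's lock. Protocol 3.7 and 9.5.1: only the DRC unblinded, with no reference to lock |
| When may the study stop? | Any time | Protocol 10.1.3: the same. No conflict |
| Which subjects form the primary analysis? | Those with data by the cutoff | Protocol 9.5.8.1: the mITT set of each cohort |
| Status of visits after the cutoff? | Exploratory | Protocol 9.5.8.2 and SAP 12.5.2: "The trial will also evaluate the following secondary endpoints at each post-baseline data collection time point" |
| Declared? | – | SAP 4.1 lists only the C-SSRS, the physical examination and the Per Protocol Set |

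**What the cutoff does**

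- A calendar cutoff during enrolment: subjects who reach +60h or Day 29 later are outside the frozen data. The primary comparison uses part of the cohort, and an analysis of all mITT subjects is exploratory under the closing rule.
- A cutoff at the primary visit, applied to every subject: the full mITT primary analysis is intact. Later visits still become exploratory (+72h, Day 11 and Day 34 in the IV-only cohorts; Days 36, 57 and 71 in Cohort 6), contrary to protocol 9.5.8.2 and SAP 12.5.2.

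**Where it can apply.** SAP 10.2 schedules the unblinded analysis of Cohorts 1-3 after the last Cohort 3 subject's final visit and lock. Cohorts 4 and 5 are optional. The practical exposure is therefore mainly Cohort 6 and any optional cohort.

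**Illustration of size.** The documents give no SD and no power calculation, so there is no figure to reproduce. Inputs:

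- Cohort size: up to about 30, allocated 1:1 (SAP 6.1), so 15 per arm.
- Criterion: 3-4 points (SAP 12.5.1).
- SD of change: assumed 6, 8 or 10 points.
- Comparison: unadjusted, with no true effect.

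Formulae: SE = SD × √(2/n per arm); P(favourable difference ≥ c) = 1 − Φ(c/SE).

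| | SD 6 | SD 8 | SD 10 |
|---|---|---|---|
| SE, full cohort (15 per arm): SD × √(2/15) | 2.19 | 2.92 | 3.65 |
| SE, cut at 10 of 30 (5 per arm): SD × √(2/5) | 3.79 | 5.06 | 6.32 |
| P(≥ 3 points), full cohort | 8.5% | 15% | 21% |
| P(≥ 3 points), cut at 10 | 21% | 28% | 32% |
| P(≥ 4 points), full cohort | 3% | 9% | 14% |

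The SE rises by a factor of √(15/5) = 1.73 whatever the SD. Under all three assumed SDs, the SE at the early cut exceeds 3 points; at SD 8 and 10 it also exceeds 4.

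**The case against.** The strongest case on the other side is that this is a descriptive Phase 2A study with documented safeguards. All efficacy is hypothesis-generating, there is no multiplicity adjustment, and protocol 9.5.8.4 describes even its preferred repeated-measures model as exploratory. The listed steps set the cutoff first, freeze the data blind and unblind afterwards. A complete set follows lock, so no result is suppressed. Calling data exploratory when they are rated after a public release is also a cautious choice, because later ratings may be influenced by expectations.

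Much of this stands. The safeguards reduce the risk, and the status of visits rated after a release is a matter for judgement. But no safeguard fixes an earliest cutoff, and the complete set does not restore the primary status of the full-cohort analysis. The SAP 10.1 sentence does sit in the section on DRC snapshots, and SAP 6.4 already gives some external statisticians treatment information. However, SAP 10.3 does not say that the people it unblinds are outside the study teams. Since the protocol does not tie blinding to lock, the conflict over unblinding before lock specifically is with SAP 10.1.

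A reader might infer that the sponsor could pick the cutoff after seeing results, which would raise the chance of a spurious 3-point difference well beyond the figures above. The documents do not support that as the expected course: the order of steps and the bar on exposed personnel are aimed against it. What remains is a gap. The bar does not expressly cover the choice of cutoff, nobody is named to make it, and the sponsor's Chief Medical Officer sits on the DRC, whose members are unblinded at its meetings (protocol 3.3 and 3.7).

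**Conclusion.** The inconsistency is real and rests on the text alone: SAP 10.3 allows earlier publication than the protocol and SAP 10.1, allows unblinding before the lock required by SAP 10.1, and is not declared in SAP 4.1. As written, a mid-enrolment calendar cutoff would replace the full-cohort mITT primary analysis with one from part of the cohort.

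The size depends on the assumed SDs and on a cut at 10 of 30 subjects: a standard error of 3.8-6.3 rather than 2.2-3.7 points. A cutoff chosen without knowledge of results costs precision only; bias arises only if it is chosen with that knowledge. The planned MMRM adjusts for baseline, so its standard errors would differ from these unadjusted ones.

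Three further inferences would go too far. The right to stop at any time is not in conflict. No type 1 error rate is breached, because none is claimed. Not every early cutoff disturbs the primary analysis, because a whole-cohort cutoff at the primary visit leaves it intact.

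Severity: minor to should-fix.

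**What to change.** Reconcile SAP 10.3 with protocol 3.7, 9.5.1 and 10.5 and with SAP 10.1. Keep the right to stop at any time, the DRC's unblinded reviews, the unblinded roles in SAP 6.4 and emergency unblinding. Then choose one of two options:

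- (a) Limit publication and all other unblinding to after completion and lock of the cohort.
- (b) Allow early topline results only once every randomised subject in the cohort has passed or missed the primary visit (+60h or Day 29). Declare this in SAP 4.1, amend the protocol to match and align SAP 10.1.

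Under either option, state that the primary analysis contains all mITT subjects of the cohort, and that any cutoff is set by named personnel without access to unblinded results from that cohort.

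Reconcile the closing rules of SAP 10.3 with protocol 9.5.8.2 and SAP 12.5.2. Later-visit data collected before any public release should stay secondary; for visits rated after a release, state the status chosen.

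Cost: SAP wording, plus a protocol amendment under (b). The sponsor gives up mid-cohort disclosure. Under (a), results wait for follow-up after the last primary visit, nominally 34 − 3 = 31 days in the IV-only cohorts or 71 − 29 = 42 days in Cohort 6, plus the time to lock. Under (b), topline results do not wait for follow-up.
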